## Appendix B Prohibited and Restricted Concomitant Medications: Inhibitors and Inducers of Cytochrome P450 Enzyme 3A4

The information presented here is intended to provide guidance and does not constitute an exhaustive list of strong CYP 3A4 enzyme (CYP3A4) inhibitors and inducers. Any questions should be discussed with the Medical Monitor or appropriate designee.

Subjects who take prohibited concomitant medications during the study will be discontinued, unless the discontinuation presents an unacceptable medical risk. The justification to allow the subject to continue in the study will be made by the Sponsor/Medical Monitor with medical input from the Investigator, and will be documented. If allowed to remain in the study, this will be reported as a major protocol deviation and not a waiver.

Inhibitors of CYP3A4 are to be stopped at least 7 days or 5 half-lives prior to study drug administration, whichever is longer. Inducers of CYP3A4 are to be stopped 30 days or 5 half-lives prior to study drug administration, whichever is longer. Moderate inhibitors and inducers of CYP3A4 may be allowed but should be used with caution. The metabolism of pimavanserin is affected by strong CYP3A4 inhibitors, resulting in an increase in maximum plasma concentration ( $C_{max}$ ) and area under the plasma concentration-time curve (AUC) of approximately 3-fold.


STRONG INHIBITORS
	
Boceprevir (Victrelis®)                      Clarithromycin (Biaxin®)                      Cobicistat (part of Stribild®)                      Conivaptan (Vaprisol®)                      Fluvoxamine (Luvox®)                      Grapefruit juicea                      Indinavir (Crixivan®)                      Itraconazole (Sporanox®)                      Ketoconazole (Nizoral®)                      Lopinavir and ritonavir (Kaletra®)                      Mibefradil (Posicor®)                      Nefazodone (Serzone®)                      Nelfinavir (Viracept®)                      Posaconazole (Noxafil®)                      Quinupristin (Synercid®)                      Ritonavir (Norvir®, part of Viekira Pak™)                      Saquinavir (Invirase®)                      Telaprevir (Incivek®)                      Telithromycin (Ketek®)                      Voriconazole (Vfend®)
	
MODERATE INHIBITORS
	
Amprenavir (Agenerase®)                      Aprepitant (Emend®)                      Atazanavir (Reyataz®)                      Ciprofloxacin (Cipro®)                      Darunavir/Ritonavir (Prezista®/Ritonavir)                      Diltiazem                      Erythromycin (Erythrocin® Lactobionate)                      Fluconazole (Diflucan®)                      Fosamprenavir (Lexiva®)                      Grapefruit juicea                      Imatinib (Gleevec®)                      Verapamil (Calan®)

---------------------------------	--	-----------------------------------	--

STRONG INDUCERS
	
Avasimibe                  Carbamazepine (Tegretol®)                  Phenobarbital (Luminal®, Solfoton®)                  Phenytoin (Dilantin®)                  Rifampin (Rifadin®, Rifadin® IV, Rimactane®)                  St. John's Wort
	
MODERATE INDUCERS
	
Bosentan (Tracleer®)                  Efavirenz (Sustiva®)                  Etravirine (Intelence®)                  Modafinil (Provigil®)                  Nafcillin (Unipen®, Nallpen®)

-------------------------------	--	---------------------------------	--

a The effect of grapefruit juice varies widely among brands and is concentration-, dose-, and preparation-dependent. Studies have shown that it can be classified as a “strong CYP3A inhibitor” when a certain preparation was used (e.g., high dose, double strength) or as a “moderate CYP3A inhibitor” when another preparation was used (e.g., low dose, single strength). (FDA Drug Development and Drug Interactions <http://www.fda.gov/Drugs/DevelopmentApprovalProcess/DevelopmentResources/DrugInteractionsLabeling/ucm093664.htm#classInhibit>).

SCOPA	Scale for Outcomes in Parkinson's Disease
SD	standard deviation
SE	standard error
SI	Système International
SOC	system organ class
SNRI	selective norepinephrine inhibitor
SSRI	serotonin reuptake inhibitor
TEAE	treatment-emergent adverse event
VAS	visual analog scale

1 INTRODUCTION

This statistical analysis plan (SAP) provides a technical and detailed elaboration of the statistical analyses of efficacy and safety data as described in Amendment 2 of the final study protocol dated 08 January 2019. Specifications for tables, figures, and listings are contained in separate documents.

2 OBJECTIVES

2.1 Primary Objective

The primary objective of this study is to assess the efficacy of pimavanserin for the treatment of depression in adults with Parkinson's disease (PD).

2.2 Secondary Objectives

The secondary objectives of this study are to explore the efficacy of pimavanserin in the following domains:

- Clinician's global assessment of treatment benefits
- Nighttime sleep and daytime sleepiness
- Quality of life (QoL)

2.3 Safety Objectives

The safety objectives of the study are to assess the safety of pimavanserin for the treatment of depression in adults with PD.

3 STUDY DESIGN

3.1 General Study Design

This study will be conducted as a Phase 2, 8-week, open-label, single arm, multi-center, outpatient study in subjects with PD and depression. Subjects can receive treatment as either a monotherapy (pimavanserin 34 mg alone), or adjunctively (pimavanserin 34 mg plus an antidepressant) if depression is inadequately controlled with current therapy.

Approximately 20 sites in the U.S will participate in this study. Subjects will participate in the study for up to 13 weeks, consisting of a screening period of up to 3 weeks, followed by a treatment period of approximately 8 weeks, and a 2-week safety follow-up (telephone call).

[figure not shown]
On the first day of the treatment phase (Baseline), eligible subjects will be enrolled and receive the first dose of adjunctive pimavanserin 34 mg per day. The remaining study

medication will be provided to the subjects to take home with instruction to take the medication at approximately the same time each day.

Clinic visits occurring after Baseline will be conducted at Weeks 2, 4, 6, and 8 (End-of-Study [EOS]/Early Termination [ET] visit).

[Figure 1](#) illustrates the study design.

Figure 1 Schematic of Study Design

3.2 Schedule of Assessments

The schedule of events and assessments for the study is presented in Table 1.

Table 1 Schedule of Events and Assessments

	Screening	Baseline	Week 2	Week 4	Week 6	EOT Week 8^g	Safety Follow-up Week 10
	Visit 1	Visit 2	Visit 3	Visit 4	Visit 5	Visit 6	Visit 7
Study Day(s)	-21 to -1	1	12 to 18	26 to 32	40 to 46	54 to 60	68 to 74
Informed consent	X						
Inclusion/exclusion assessment	X	X					
MGH ATRQ ^a	X						
Medical history and demographics	X						
Weight, height, BMI	X	X ^f				X ^f	
Physical and neurological examination	X					X	
12-lead ECG ^b	X	X	X			X	
Vital signs ^c	X	X	X	X	X	X	
Clinical laboratory tests ^d	X	X				X	
Screen for drugs of abuse	X	X					
Pregnancy test ^e	X	X				X	
HAMD-17	X	X	X	X	X	X	
C-SSRS	X	X	X	X	X	X	
MMSE	X	X		X		X	
CGI-I			X	X	X	X	
CGI-S		X	X	X	X	X	
SCOPA		X		X		X	
EQ-5D-5L		X		X		X	
UPDRS Part III		X		X		X	
Dispense study drug		X		X			

Study drug accountability			X	X	X	X	
Phone Follow-Up							X
Concomitant medication	X	X	X	X	X	X	X
AE assessment	X	X	X	X	X	X	X

Abbreviations: AE=adverse event; BMI=body mass index; C-SSRS=Columbia Suicide Severity Rating Scale; CGI-I=Clinical Global Impression-Improvement; CGI-S=Clinical Global Impression-Severity; ECG=electrocardiogram; EOT=end of treatment; EQ-5D-5L-5L=EuroQol 5 dimensions-5 levels; HAMD-17=Hamilton Depression Scale-17 Item; MGH ATRQ=Massachusetts General Hospital Antidepressant Treatment Questionnaire; MMSE=Mini-Mental State Exam; SCOPA=Sleep Scales for Outcomes in Parkinson's Disease-Sleep ; UPDRS Part III=Unified Parkinson's Disease Rating Scale Part III.

Notes:

- ^a Applicable only to subjects who are currently taking an antidepressant.
- ^b 12-lead ECG at Screening is to be completed in triplicate within a 3 minute period. The ECG may be repeated once at Screening in consultation with the Medical Monitor. Single ECG recordings are to be collected at subsequent visits. ECGs can be performed any time before blood sampling or at least 30 minutes after blood sampling during clinic visits
- ^c Vital signs (sitting or supine [at least 3 minutes] blood pressure, pulse rate, oral temperature, and respiratory rate) will be performed at Screening and each study visit.
- ^d Thyroid-stimulating hormone (TSH) will only be assessed at Screening. TSH will not be analyzed as part of the chemistry serum testing at other study visits.
- ^e Applicable only to women of childbearing potential. A serum pregnancy test is performed at Screening and a urine pregnancy test at Baseline and Week 8.
- ^f Only weight will be measured after Screening.
- ^g Subject terminating early should at a minimum complete assessments of safety (vital signs, ECG, AEs, clinical laboratories, C-SSRS) and, if possible, complete all Week 8 assessments.

3.3 Randomization

Not applicable.

3.4 Blinding

This is an open-label study. Subjects, site staff, and the sponsor will be aware that the subject is being treated with a 34 mg dose of pimavanserin.

3.5 Determination of Sample Size

The initial sample size calculation was based on a standard deviation of 8.0 and a dropout rate of 10%. An interim review of the statistical assumptions was conducted after 9 subjects completed the Week 8 visit, and the sample size was recalculated. The standard deviation in HAMD-17 total score change from Baseline to Week 8 was observed to be lower, and the dropout rate higher, than the initial assumptions. Therefore, the sample size has been recalculated as follows.

Assuming the standard deviation for the change in HAMD-17 total score from Baseline to Week 8 is 6.0 points, 34 evaluable subjects will provide 80% power to detect a minimum mean reduction of 3 points from Baseline to Week 8 at a significance level of 0.05 using a 2-sided paired t-test.

Adjusting for a potential non-evaluable rate of up to 15%, approximately 40 subjects will be enrolled.

4 ANALYSIS SETS

4.1 Safety Analysis Set

The Safety Analysis Set will consist of a subset of enrolled subjects who received at least one dose of study drug (pimavanserin).

4.2 Full Analysis Set

The Full Analysis Set will consist of a subset of subjects in the Safety Analysis Set who have both a Baseline value and at least one post-Baseline value for the HAMD-17 total score.

5 DATA HANDLING CONVENTIONS

All data collected in the study will be listed.

5.1 General Data Reporting Conventions

5.1.1 Continuous Variables

For continuous variables, the following summary statistics will be provided: number of subjects, mean, standard error of the mean (SE), standard deviation (SD), minimum, maximum, and median. Unless specified otherwise, means, medians, and confidence intervals (CIs) will be presented to one more decimal place than the raw data, and the standard deviations and standard errors will be presented to 2 more decimal places than the raw data.

5.1.2 Categorical Variables

For categorical variables, summaries will include the number and percentage of subjects in each category, using the number of subjects with non-missing values as the denominator for the percentages (unless otherwise specified). Categories with zero counts will not have zero percentages displayed. Percentages will be presented to 1 decimal place.

5.1.3 Statistical Tests

Unless specified otherwise, all statistical tests will be 2-sided hypothesis tests performed at the significance level of 5% for main effects and all confidence intervals (CIs) will be 2-sided 95% CIs. P-values will generally be presented to 4 decimal places; p-values less than 0.0001 will be presented as <0.0001.

5.1.4 Conversion of Days to Months

When converting number of days to months, it will be calculated as the number of days divided by 365.25 and then multiplied by 12. When converting number of days to years, it will be calculated as the number of days divided by 365.25.

5.2 Derived Variables

In general, the total scores and subscores for assessment scales will be derived within the analysis datasets. In the event that total scores and/or subscores are also collected on the electronic case report form (eCRF), the derived values will be used for all analyses. Both the raw and derived scores will be presented in listings.

5.2.1 Hamilton Depression Rating Scale 17-Items (HAMD-17)

The HAMD-17 is assessed at Screening, Baseline, Weeks 2, 4, 6, and Week 8/ET visits.

The HAMD-17 is a 17-item clinician-administered questionnaire used to provide an indication of depression, and as a guide to evaluate recovery (Hamilton, 1960). The

questionnaire assesses symptoms over the past week (7 days). The questionnaire is designed for adults to rate the severity of, and change in, depressive symptoms by probing mood, feelings of guilt, suicide ideation, insomnia, agitation or retardation, anxiety, weight loss, and somatic symptoms. Each item on the questionnaire is scored on a 3- or 5-point scale, depending on the item, and the total score is compared to the corresponding descriptor. The HAMD-17 total score can range from a minimum of 0 to a maximum of 52. A score of 0-7 is considered normal. Scores of 14 or higher indicate moderate, severe, or very severe depression.

If more than 3 items are missing, the total score will be set to missing. If 3 or fewer items are missing, then missing items will be imputed as follows:

- Items using a 3-point scale (4, 5, 6, 12, 13, 14, 16, and 17): missing values will be imputed using the arithmetic mean of the non-missing items that are also scored on a 3-point scale, then rounded to the nearest integer
- Items using a 5-point scale (1, 2, 3, 7, 8, 9, 10, 11, and 15): missing values will be imputed using the arithmetic mean of the non-missing items that are also scored on a 5-point scale, then rounded to the nearest integer

5.2.2 Clinical Global Impression – Severity (CGI-S) Scale

The CGI-S is assessed at Screening, Baseline, Weeks 2, 4, 6, and 8/ET visits.

The CGI-S is a clinician-rated, 7-point scale that is designed to rate the severity of the subject's depression at the time of assessment using Investigator's judgment and past experience with subjects who have the same disorder (i.e., depression in Parkinson's disease). The 7-point scores are: 1=normal, not ill; 2=minimally ill; 3=mildly ill; 4=moderately ill; 5=markedly ill; 6=severely ill; 7=among the most severely ill.

Missing CGI-S scores will not be imputed.

5.2.3 Clinical Global Impression– Improvement (CGI-I) Scale

The CGI-I is assessed at Weeks 2, 4, 6, and 8/ET visits.

The CGI-I is a clinician-rated, 7-point scale that is designed to rate the improvement in the subject's depression at the time of assessment, relative to the symptoms at Baseline. The 7-point scores are: 1=very much improved; 2=much improved; 3=minimally improved; 4=no change; 5=minimally worse; 6=much worse; 7=very much worse.

Missing CGI-I scores will not be imputed.

5.2.4 Scale for Outcomes in Parkinson's Disease (SCOPA) – Sleep Scale

The SCOPA-Sleep scale is assessed at Baseline, Week 4, and Week 8/ET visits.

The SCOPA-Sleep was developed for research in Parkinson's disease to evaluate both nighttime sleep (NS) and daytime sleepiness (DS). The SCOPA-Sleep scale consists of 3 subscales, SCOPA-NS, SCOPA-DS, and one additional question that evaluates overall sleep quality. For each subscale, the time frame is the preceding month.

The SCOPA-NS subscale addresses problems in nighttime sleep and consists of 5 items: sleep initiation, sleep fragmentation, sleep efficiency, sleep duration, and early wakening. Each item has 4 response options (ranging from 0=not at all, to 3=a lot) such that the minimum score is 0 and the maximum score is 15, with higher scores indicating more severe NS problems.

The SCOPA-DS subscale addresses problems in daytime sleepiness and consists of 6 items: how often the subject 1) fell asleep unexpectedly, 2) fell asleep peacefully, 3) fell asleep watching TV/reading, 4) fell asleep while talking to someone, 5) had difficulty staying awake, and 6) whether falling asleep in the daytime was considered a problem. Each item has 4 response options (ranging from 0=never, to 3=often). Therefore, possible SCOPA-DS subscale scores can range from 0 to 18, with higher scores indicating more severe DS problems.

If only one SCOPA-NS item is missing, then the subscale score will be imputed by replacing the missing item with the mean (rounded to the nearest integer) of the non-missing items for a given subject and timepoint. If more than 1 item is missing, then the subscale total score will remain missing. The same imputation algorithm will be applied to the SCOPA-DS subscale.

Global sleep quality is assessed using a single-item 7-point scale (1=slept very well to 7=slept very badly). This item will not be included in the SCOPA-DS or SCOPA-NS total scores. Missing values for the global sleep quality items will not be imputed.

5.2.5 EQ-5D-5L Proxy Version 1

The EQ-5D-5L questionnaire is assessed at Baseline, Week 4, and Week 8/ET.

The EQ-5D-5L is a standardized measure of health status that provides a simple, generic measure of health for clinical and economic appraisal. In this study, Proxy Version 1 will be administered, in which the caregiver (the proxy) is asked to rate the subject's health-related quality of life in his/her (the proxy's) opinion. This questionnaire consists of 2 components – the EQ-5D-5L descriptive system and the EQ-5D-5L Visual Analogue scale (EQ-5D-5L VAS).

The descriptive system consists of 5 dimensions: mobility, self-care, usual activities, pain/discomfort, and anxiety/depression. Each dimension has 5 levels (responses): no problem (1), slight problems (2), moderate problems (3), severe problems (4), and extreme problems (5). The digits for the 5 dimensions are combined into a 5-digit code that describes the subject's health state.

The EQ-5D-5L VAS records the subject's health on a vertical visual analogue scale, where the upper endpoint is labeled "The best health you can imagine" and is numbered 100, while the lower endpoint is labeled "The worst health you can imagine" and is numbered 0. The EQ-5D-5L VAS will be treated as a continuous endpoint.

Missing values will not be imputed for either the descriptive system or EQ-5D-5L VAS.

5.2.6 Columbia-Suicide Severity Rating Scale (C-SSRS)

The C-SSRS is assessed at Screening, Baseline, Weeks 2, 4, 6, and 8/ET visits.

The C-SSRS Baseline/Screening version will be completed at the Screening visit and the version assessing information since the last visit will be completed at Baseline, Week 2, Week 4, Week 6, and Week 8/ET.

The C-SSRS monitors changes in suicidal thinking and behavior over time in order to determine risk. Four constructs are measured: the severity of ideation, the intensity of ideation, behavior, and lethality.

There are 5 questions about suicidal ideation: wish to be dead; non-specific active suicidal thoughts; active suicidal ideation with any methods (not plan) without intent to act; active suicidal ideation with some intent to act, without specific plan; active suicidal ideation with specific plan and intent. If a subject answers "yes" to any of these 5 questions, this subject will be counted as having suicidal ideation.

There are 5 questions about suicidal behavior: suicide, actual attempt; interrupted attempt; aborted attempt; preparatory acts or behavior. If a subject answers "yes" to any of these 4 questions, this subject will be counted as having suicidal behavior.

Missing values will not be imputed.

5.2.7 Movement Disorders Society-Unified Parkinson's Disease Rating Scale Part III

The Movement Disorders Society-Unified Parkinson's Disease Rating Scale (MDS-UPDRS) Part III (motor examination) will be assessed at Baseline, Week 4, and Week 8/ET.

The MDS-UPDRS Part III is used to assess motor signs of PD and consists of 33 individual items based on 18 domains, due to left, right, and other body distributions. Each item has

5 possible responses (0, 1, 2, 3, and 4) with 0 being normal and 4 severe. The total score will be derived as the sum of the 33 item scores; thus, the total score has a potential range from 0 to 132, with higher scores indicating more severe extrapyramidal symptoms.

If 6 or fewer items are missing, then the total score for a given subject and timepoint will be imputed as the mean of the non-missing items multiplied by 33 and rounded to the nearest integer. If more than 6 items are missing, the total score will not be derived.

In addition, the MDS-UPDRS Part III assesses motor signs with the Hoehn and Yahr Stage on a 6-point scale, where asymptomatic is scored 0 and wheelchair bound or bedridden is scored 5. Missing values for Hoehn and Yahr Stage will not be imputed.

5.2.8 Mini-Mental State Examination (MMSE)

The MMSE is assessed at Screening, Baseline, Week 4, and Week 8/ET.

The MMSE is a 30-item questionnaire that includes simple questions and problems in the following areas: time and place of testing, repeating lists of words, arithmetic, language use and comprehension, and copying or drawing.

Each of the 30 items has 2 possible values, 0 (incorrect) or 1 (correct). The MMSE total score will be derived as the sum of the 30 item scores, thus the total score has a potential range of 0 to 30. Lower scores indicate more severe cognitive impairment.

If 6 or fewer items are missing, then the total score for a given subject and timepoint will be imputed as the mean of the non-missing items multiplied by 30 and rounded to the nearest integer. If more than 6 items are missing, the total score will not be derived.

5.3 Analysis Visit Windows

Baseline will be defined as the last non-missing result, including results from repeated and unscheduled measurements, before dosing.

Efficacy and safety assessments will be summarized by analysis visit as shown in [Table 2](#) below.

Table 2 Analysis Visit Windows

Analysis Visit Name	Study Visit	Target Study Day ¹	Study Day Interval
Baseline	Visit 2 (Baseline)	1	≤ 1
Week 2	Visit 3 (Week 2)	15	2 to 21
Week 4	Visit 4 (Week 4)	29	22 to 35
Week 6	Visit 5 (Week 6)	43	36 to 49
Week 8	Visit 6 (Week 8/ET)	57	50 to 63
Follow-up	Visit 7 (Week 10/Safety Follow-up)	71	≥ 64

¹ Study day = assessment date - first dose date + 1 if the assessment date \geq first dose date, otherwise study day = assessment date - first dose date. Study day 1 is the day of first administration of study drug (pimavanserin).

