5.3.1 Unscheduled Assessments

Both scheduled and unscheduled assessments, including the assessments at ET visits, will be considered for planned timepoint analyses. All assessments will be presented in data listings.

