5.3.2 Multiple Measurements within Visit Windows

If more than one assessment falls within a given window, then the assessment closest to the target study day will be selected for the by-visit summaries. If two assessments are equidistant from the target day, then the chronologically last assessment will be used. Exceptions may be made for incomplete assessments, in which case, more complete assessments may be given priority. Details are provided in a separate programming conventions document.

For safety analysis where the most extreme values should be selected (e.g., overall post-baseline minimum, overall post-baseline maximum, and potentially clinically important values), all non-missing post-Baseline values will be considered, regardless of whether the value is selected for the by-visit summaries. All results will be presented in data listings.

When the 12-lead electrocardiogram (ECG) is collected in triplicate, the average of the triplicate parameter values will be considered as one assessment for the summaries.

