14.6 Other Safety Variables

14.6.1 MMSE

The MMSE total score will be summarized by timepoint (Baseline, Week 4, and Week 8) using descriptive statistics. The change from Baseline scores will also be summarized descriptively at Week 4 and Week 8. In addition, the MMSE total score change from Baseline will be analyzed using an MMRM similar to the primary efficacy endpoint. The dependent variable will be the MMSE total score change from baseline, and the independent variables in the model will include the following: visit (Weeks 4 and 8), Baseline MMSE total score (continuous covariate), and Baseline MMSE total score-by-visit interaction.

The individual item scores will be listed but not summarized.

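### MMSE and MDS-UPDRS Part III totals collected at early termination on Days 2–21 or 36–49 enter no summary or model that the SAP specifies

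*SAP*

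**What the plan says.** SAP 5.3 applies one windowing rule to efficacy and safety data alike: "Efficacy and safety assessments will be summarized by analysis visit as shown in" Table 2. The table gives each analysis visit a study day interval: Week 2 is Days 2–21, Week 4 is Days 22–35, Week 6 is Days 36–49 and Week 8 is Days 50–63. In the Week 8 row the study visit is labelled "Visit 6 (Week 8/ET".

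SAP 5.3.1 adds that scheduled and unscheduled results, "including the assessments at ET visits, will be considered for planned timepoint analyses", and that "All assessments will be presented in data listings". Where a window holds several values, SAP 5.3.2 states that "the assessment closest to the target study day will be selected for the by-visit summaries".

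On collection, SAP 5.2.8 says: "The MMSE is assessed at Screening, Baseline, Week 4, and Week 8/ET". SAP 5.2.7 gives MDS-UPDRS Part III the same post-Baseline schedule. On analysis, SAP 14.6.1 says: "The MMSE total score will be summarized by timepoint (Baseline, Week 4, and Week 8) using descriptive statistics". Its MMRM has Weeks 4 and 8 as the only visits. SAP 14.6.2 does the same for the MDS-UPDRS Part III total, and Protocol 9.9.9 names the same time points.

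**The concern.** Both scales are scheduled at Week 4 and at Week 8/ET, so the design itself can produce a total on almost any day of treatment. The windowing rule then assigns some of those totals to Week 2 or Week 6, and neither is an analysis time point for these scales. SAP 5.3.1 shows that early-termination values are meant to be used, but it gives no rule for moving one to a visit that is analysed.

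MMSE and UPDRS Part III are named safety endpoints in Protocol 2.3.1. Subjects who stop early are the ones a safety reader would want to see, yet a collected cognitive or motor score from such a subject could be missing from every table. The label in the Week 8 row adds ambiguity, because a programmer could read it as sending every early-termination value to Week 8.

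**Working it through.** The plan gives no figure for this point. The one stated figure used as a base is enrolment in SAP 3.5, which reproduces: 34 / (1 − 0.15) = 40.

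**Step 1. Map the day of early termination (ET) to an analysis visit.**

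| ET study day | Table 2 visit | Days in window | Time point in SAP 14.6.1 and 14.6.2? |
|---|---|---|---|
| 2–21 | Week 2 | 20 | No |
| 22–35 | Week 4 | 14 | Yes |
| 36–49 | Week 6 | 14 | No |
| 50–63 | Week 8 | 14 | Yes |

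Before the Week 8 window opens there are 48 possible days (Days 2–49). On 20 + 14 = 34 of them (70.8%) the total belongs to a visit that is not analysed.

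**Step 2. Look for another route into a table.**

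- LOCF (SAP 12.3, 13.1.2 and 13.1.10) is confined to efficacy variables.
- The rule in SAP 5.3.2 that uses all post-Baseline values applies where extremes are selected. SAP 14.6.1 and 14.6.2 plan no such analysis.
- Laboratory values, vital signs, ECG and C-SSRS each have an overall post-Baseline summary (SAP 14.2, 14.3, 14.4 and 14.6.3). These two totals have none.

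Only the listings remain.

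**Step 3. Separate the two kinds of loss.** A subject who stops on Days 2–21 normally has no other post-Baseline total (an *only value*). A subject who stops on Days 36–49 normally keeps a Week 4 total and loses the later one (a *second value*).

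**Step 4. Illustrate the size.** The documents do not give the number or timing of early terminations, so these inputs are assumptions:

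- Early terminators, n: 0.10 × 40 = 4 and 0.15 × 40 = 6. The initial 10% dropout rate and the up-to-15% non-evaluable rate in SAP 3.5 serve as proxies.
- Timing: even over Days 2–53, which is 52 days, because the scheduled Visit 6 window opens on Day 54. The share on Days 2–21 is 20/52 = 38.5%, and on Days 36–49 it is 14/52 = 26.9%.
- Completion of the scale at ET, c: 1 or 0.5. Note g to SAP Table 1 leaves these scales out of the minimum ET set and asks for them only where possible.

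With f the share of terminations in the window, the expected number is n × c × f. Treating subjects as independent, P(at least one) = 1 − (1 − c × f)^n.

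| n | c | Only values expected | P(at least one only value) | Second values expected |
|---|---|---|---|---|
| 4 | 1 | 4 × 0.385 = 1.5 | 1 − (1 − 20/52)^4 = 85.7% | 4 × 0.269 = 1.1 |
| 6 | 1 | 6 × 0.385 = 2.3 | 1 − (1 − 20/52)^6 = 94.6% | 6 × 0.269 = 1.6 |
| 4 | 0.5 | 4 × 0.5 × 0.385 = 0.8 | 1 − (1 − 0.5 × 20/52)^4 = 57.4% | 4 × 0.5 × 0.269 = 0.5 |
| 6 | 0.5 | 6 × 0.5 × 0.385 = 1.2 | 1 − (1 − 0.5 × 20/52)^6 = 72.2% | 6 × 0.5 × 0.269 = 0.8 |

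**Step 5. Relax the even spread.** Let 20% to 60% of terminations fall on Days 2–21.

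- Low end (n = 4, c = 0.5, f = 0.20): 4 × 0.5 × 0.20 = 0.4 only values, P = 1 − 0.90^4 = 34.4%.
- High end (n = 6, c = 1, f = 0.60): 6 × 0.60 = 3.6 only values, P = 1 − 0.40^6 = 99.6%.

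**The case against.** The strongest reply is that the SAP is not the whole specification. SAP 1 leaves table specifications to separate documents, and SAP 5.3.2 refers to a programming conventions document. Neither is available here, and either could hold a rule for early-termination values. This limits the claim to what the SAP specifies. It does not remove the gap, because nothing in the SAP says those documents reassign such values, and a rule that decides whether a safety endpoint is tabulated belongs in the SAP.

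A second reply is that the Week 8/ET label only names the clinic visit and that the interval column governs. That is the better reading, and it is the one under which the values drop out. If the label governed instead, a HAMD-17 score from a Day 10 termination would enter the primary model as Week 8, which is a larger problem. Either way, one clarifying sentence is worth having.

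Third, these scales are not alone. Physical and neurological examinations (SAP 14.5) are also summarised only at Screening and Week 8. That is so, and the change proposed here does not reach them.

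Fourth, the precedents for laboratory values, vital signs and ECG use extremes or flags, whereas a last-value table does not show a subject's worst score. That is also correct. A last-value table still suits the purpose, because the excluded early-termination score is normally the subject's last.

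Finally, the size is uncertain and the consequence small. The range in Step 5 is wide, and SAP 3.5 reports that dropout at the interim review exceeded the initial 10%, so 4 terminators may be too few. With about 40 subjects the listings can be read in full. These points stand and keep the priority low.

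**Conclusion.** The concern holds for the two total scores. Under the Table 2 day intervals, an early-termination MMSE or MDS-UPDRS Part III total from Days 2–21 or 36–49 enters no summary or MMRM that the SAP specifies.

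Under an even spread, roughly one or two subjects per scale would lose their only post-Baseline total. That estimate rests on proxy dropout rates, assumed timing and assumed completion at termination, none of which the documents establish.

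The severity is low. Nothing in the documents shows that these subjects score worse, and worsening reported as an adverse event still reaches the TEAE tables. The primary HAMD-17 analysis is unaffected under the day intervals because it models all four post-Baseline visits. Hoehn and Yahr Stage is summarised by visit with no visits named, so it may not be affected.

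**What to change.** Add to SAP 14.6.1 and 14.6.2:

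> *Change from Baseline to the last post-Baseline total score will be summarized descriptively using all non-missing post-Baseline values, including ET and unscheduled assessments, regardless of analysis visit window.*

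Add to SAP 5.3:

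> *The study day interval, not the Week 8/ET label, determines the analysis visit for the by-visit summaries and MMRM.*

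The Table 2 intervals, the Week 4 and Week 8 models and the LOCF rules stay as they are.

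The cost is these two sentences and one small descriptive table per scale, with no new data. The drawback is that last values come from differing study days, so the new tables should supplement the Week 4 and Week 8 tables and not replace them.
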